### 4.2. Subgroups

Not applicable for this study.

|  |                           |                  |                |
|--|---------------------------|------------------|----------------|
|  | Form               | Form Nr.  | 1M-DMST-011-A3 |
|  | Statistical Analysis Plan | Page      | 14 of 116      |
|  |                           | Version # | 0.1            |

## 5. General Definitions and Naming Conventions

To avoid ambiguity during the analysis, a few definitions and conventions for data handling are described here.

### 5.1. Treatment Group Names and Labels

Due to the single-arm nature of the stage, no treatment group definition or label is required.

### 5.2. General Methodology and Presentation of the Results

All collected data will be presented through listings and tables.

To ensure effective presentation of results, if deemed necessary, listings shall be divided into two or more distinct outputs. Each newly created listing will maintain the original table number, followed by a consecutive alphabetical letter, and the original title; additional specifications regarding the contents of the listing may be included after the listing title.

In tables, default summary statistics for quantitative variables will be:

- Mean, Standard Deviation (SD), number of missing observations (N), minimum and maximum values, if all continuous variables of a specific section (i.e., vital signs, blood evaluation, etc.) could be considered normal;
- Median, Range Q1 - Q3, number of missing observations (N), minimum and maximum values, if at least one continuous variable of a specific section (i.e., vital signs, blood evaluation, etc.) couldn't be considered normal.

For simplicity, the mockup tables in this SAP use the first case. However, the final study report will reflect the appropriate case based on the data distribution.

For qualitative variables, the counts (N) and percentage (%) of patients with non-missing data per category will be the default summary presentation, and, where appropriate and present, the number of missing values as a "Missing" category.

Percentages will be calculated using as the denominator the number of all patients in a specified population or treatment group, unless specified otherwise. The denominator will be specified in a footnote to the tables for clarification if necessary.

All listings will be produced with reference to the set of All patients.

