#### Risks associated with the BCL device

5. The needles used to deploy the hook wires may be placed through the chest wall into the lung, causing a pneumothorax.  
*Likelihood:* the BCL is designed to prevent needle tips from getting close to the lung.  
*Clinical consequences:* Subjects who developed respiratory symptoms and had a pneumothorax diagnosed by chest x-ray would be treated with transient placement of a small diameter chest tube.
6. The BCL may introduce an additional infection risk.  
*Likelihood:* although the BCL could have the potential to introduce additional infection risk, the BCL is sterile and is used in a sterile field in the operating room.  
*Clinical consequences:* cellulitis would require antibiotic treatment; an abscess would require incision and drainage and antibiotics.
7. The BCL may inaccurately localize the cancer, causing the Investigator to miss the cancer or excise it with a higher-than-expected positive margin rate.  
*Likelihood:* in the Dartmouth clinical trial of *supine* MRI/intraoperative scanning and tracking technique, 66 of 67 (99%) tumors were successfully localized and removed. The BCL incorporates design features (central wire) that further mitigate this risk. In the pilot BCL study of 19 subjects, tumors were localized very accurately: the median distance from the central wire to the tumor center was < 5 mm and all tumors were excised with negative margins [20].  
*Clinical consequences:* the Subject would require a second surgery to identify the cancer or re-excise the positive margin.

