### 1.2.3. Sample Size

The positive margin rate (PMR) with the use of BCL is expected to be < 5% based on a previous study [2]. Assuming a true PMR of 3% and applying the exact or Clopper-Pearson method for a single binomial proportion then a sample size of N=35 patients who have undergone surgery with the BCL and have had a margin assessment will achieve a confidence interval with total width of 15%. The upper limit of this confidence interval (18%) is lower than the currently observed positive margin rate using the standard of care.

An exact binomial confidence interval will be calculated using the actual PMR. The withdrawal of patients before the surgery with BCL will be considered as drop-out.

Statistical power calculation was performed using SAS® software [1], version 9.4.

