## 4. Analysis Sets and Subgroups

### 4.1. Analysis sets

The data sets defined for the study in accordance with the study protocol are outlined in the following table.

|                            |   |
|----------------------------|---|
| Safety Analysis Set (SAS): | The "Safety Set" will include All patients undergoing surgery with the BCL System.  |
| Full Analysis Set (FAS):   | The "Full Analysis Set" will include All patients undergoing surgery with the BCL System.   |
| Per-Protocol Set (PPS):    | The "Per-Protocol Set (PPS)" will include all the FAS patients who (a) met all inclusion/exclusion criteria liable to affect the performance assessment, (b) did not present serious deviations of the protocol that may affect efficacy. |

Definition of major protocol deviations and selection of subjects accordingly will be performed prior to Database Lock (DBL).

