#### Collected Variables:

- Was surgery performed? (Yes/No) [CRF –V2]
- If No, please specify the reason (free text) [CRF –V2]  
If Yes:
- Date of surgery (dd-mmm-yyyy) [CRF –V2]
- Was Tumor specimen removed? (Yes/No) [CRF –V2]
- If No, please specify the reason (free text) [CRF –V2]  
If Yes:
- Was specimen mammogram obtained? (Yes/No) [CRF –V2]
- If No, please specify the reason (free text) [CRF –V2]
- Was tumor specimen sent to the pathologist for evaluation of the positive margins? (Yes/No) [CRF –V2]
- If No, please specify the reason (free text) [CRF –V2]
- Were positive margins detected? (Yes/No) [CRF –V2]

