#### Analysis of Primary Efficacy variable:

To evaluate the performance of BCL in reducing the positive margin rate, exact . 95% Confidence Interval (CI) for positive margin rate (PMR) using the Clopper-Pearson method will be estimated with actual positive margin rate calculated at V2

The primary analysis will be performed on both FAS and PPS. The analysis performed on PPS will be obtained to support the results on FAS.

Moreover, bar plots will be presented to show the positive margin rate distribution.

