**Table 14. Surgery and positive margin evaluation**

**Full Analysis Set, Per Protocol Set**

|  |              | FAS
(N=XX) | PPS
(N=XX) |
|--|--------------|-----------------------|-----------------------|
| Surgery performed?  |              |                       |                       |
| Yes   | N (%) | X (XX.X)              | X (XX.X)              |
| No  | N (%) | X (XX.X)              | X (XX.X)              |
| Missing   | N (%) | X (XX.X)              | X (XX.X)              |
| Tumor specimen removed?   |              |                       |                       |
| Yes   | N (%) | X (XX.X)              | X (XX.X)              |
| No  | N (%) | X (XX.X)              | X (XX.X)              |
| Missing   | N (%) | X (XX.X)              | X (XX.X)              |
| Specimen mammogram obtained   |              |                       |                       |
| Yes   | N (%) | X (XX.X)              | X (XX.X)              |
| No  | N (%) | X (XX.X)              | X (XX.X)              |
| Missing   | N (%) | X (XX.X)              | X (XX.X)              |
| Tumor specimen sent to the pathologist for evaluation of the positive margins |              |                       |                       |
| Yes   | N (%) | X (XX.X)              | X (XX.X)              |
| No  | N (%) | X (XX.X)              | X (XX.X)              |
| Missing   | N (%) | X (XX.X)              | X (XX.X)              |
| Positive margins detected   |              |                       |                       |
| Yes   | N (%) | X (XX.X)              | X (XX.X)              |
| No  | N (%) | X (XX.X)              | X (XX.X)              |
| Missing   | N (%) | X (XX.X)              | X (XX.X)              |
| 95% Confidence Interval   |              | (XX.XX – XX.XX)       | (XX.XX – XX.XX)       |
| FAS: Full Analysis Set
PPS: Pere Protocol Set                                     |              |                       |                       |

|  |                           |                  |                |
|--|---------------------------|------------------|----------------|
|  | Form               | Form Nr.  | 1M-DMST-011-A3 |

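### The SAP leaves the PMR denominator in conflict, and a cancer missed by BCL guidance cannot enter the PMR numerator under either reading

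*SAP*

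**What the plan says.** **Denominator.** SAP 5.2 gives the only explicit rule: "Percentages will be calculated using as the denominator the number of all patients in a specified population or treatment group, unless specified otherwise". SAP 4.1 defines the FAS as every patient operated with the BCL and does not require a margin result. SAP 6.2.1 states that "The primary analysis will be performed on both FAS and PPS", names the Clopper-Pearson method, and lists imputation as not applicable. The Table 14 shell (numbered 13 in the SAP 9.1 contents list) has a column headed with the FAS N. Under "Positive margins detected" it prints Yes, No and Missing, each as a count with a percentage.

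Other text points elsewhere. SAP 5.2 also says that "the counts (N) and percentage (%) of patients with non-missing data per category will be the default summary presentation". SAP 1.2.3 plans for "N=35 patients who have undergone surgery with the BCL and have had a margin assessment". Protocol 2.5.5 rules out imputation unless the SAP describes it, and asks that available data be used.

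**Missed tumour.** Protocol 2.11.3 lists this device risk: "The BCL may inaccurately localize the cancer, causing the Investigator to miss the cancer or excise it with a higher-than-expected positive margin rate". Protocol Appendix 1 defines a positive margin only by cancer on the inked edge or, for pure DCIS, less than 2 mm from it. In SAP 6.2.1 the margin item is reached only after a Yes to "Was Tumor specimen removed? (Yes/No)". The lumpectomy histology item in SAP 6.2.2 offers DCIS, IBC or both, and has no response for a specimen without tumour.

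**The concern.** Two programmers following this SAP could produce two different primary results. One would divide by the FAS N and the other by the number of patients with a margin result. If the FAS N is used, a patient whose margin was never assessed sits in the denominator, can never be in the numerator, and so dilutes the rate.

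The second gap is more serious. The PMR is meant to show how well BCL guidance works. If guidance misses the cancer, there is either no tumour specimen, so the margin item stays blank, or a specimen with no cancer near its edge, which does not meet the Appendix 1 definition. In both cases the failure that, by the protocol's own account, would need a second operation does not count against the device in the only primary endpoint. A rule chosen after the results are known would carry little weight.

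**Working it through.** **Inputs**
- N = 35, assumed PMR 3%, interval width 15%, quoted upper limit 18%: SAP 1.2.3.
- 66 of 67 tumours localized and removed with a related supine-MRI technique: Protocol 2.11.3.
- Numbers of positive margins, misses and unassessed margins: my assumptions, shown as a range. FAS = 35 is also an assumption for illustration.

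**Formula.** For x events in n patients, the two-sided 95% Clopper-Pearson limits are the 0.025 quantile of Beta(x, n − x + 1) and the 0.975 quantile of Beta(x + 1, n − x). The lower limit is 0 if x = 0.

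**Step 1: the plan's own figure.** At x = 0.03 × 35 = 1.05, the limits are 0.09% and 15.14%, a width of 15.05%. At x = 1, they are 0.07% and 14.92%, a width of about 14.84%. The stated 15% width is reproduced. The 18% is not a Clopper-Pearson limit for this case; it equals 3% + 15%. I use 18% below only because the SAP compares it with the standard-of-care rate.

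**Step 2: one positive margin, k patients with a missed tumour or no margin result, FAS = 35.** The k patients are taken to have a blank margin item.

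| k | All FAS, 1/35 | Assessed only, 1/(35 − k) | k counted as failures, (1 + k)/35 |
|---|---|---|---|
| 1 | 2.86% (0.07–14.92) | 1/34 = 2.94% (0.07–15.33) | 2/35 = 5.71% (0.70–19.16) |
| 2 | 2.86% (0.07–14.92) | 1/33 = 3.03% (0.08–15.76) | 3/35 = 8.57% (1.80–23.06) |
| 3 | 2.86% (0.07–14.92) | 1/32 = 3.12% (0.08–16.22) | 4/35 = 11.43% (3.20–26.74) |

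**Step 3: split the two effects.** For k = 1 to 3, the choice of denominator alone changes the rate by 0.08 to 0.26 points (2.94 − 2.86; 3.12 − 2.86). Counting a miss in the numerator adds 1/35 = 2.86 points per patient. If tumour-free tissue is sent and the margin item is answered No, that patient is assessed and non-positive, so the result is 1/35 under both denominators. Choosing the denominator therefore does not solve the missed-tumour problem.

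**Step 4: how likely is a miss?** At 1/67 per patient, P(at least one in 35) = 1 − (66/67)^35 = 0.41. The exact 95% interval for 1/67 is 0.04% to 8.04%. Putting those limits into 1 − (1 − p)^35 gives about 1% to 95%. The 41% is an illustration, not an estimate for this device.

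**The case against.** A reader might infer that the SAP firmly divides the PMR by all FAS patients and so records unassessed margins as clear. The documents do not support that. The non-missing wording in SAP 5.2, the assessed-patient sample size in SAP 1.2.3 and the available-data rule in Protocol 2.5.5 all point the other way, and SAP 5.2 allows a footnote to state the denominator. Table 14 keeps Missing apart from No, so a reader could recompute the rate. What stands is that the wording conflicts and the interval's denominator is never stated. The effect of that alone is small.

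A reader might also infer that any poor localization escapes the endpoint. It does not. Inaccurate guidance that leaves cancer at the edge does raise the PMR. In the BCL pilot (Protocol 2.11.1) one of 19 cancers was inaccurately localized, yet every tumour was removed with negative margins. The gap concerns a specimen that does not contain the cancer. That such a case would be entered as No is my inference from Appendix 1; neither document says so.

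Misses may also surface elsewhere: the specimen radiograph checks for the biopsy clip, reasons for no specimen are listed, device deficiencies are tabulated, and Protocol 2.11.5 says inaccurate localization will be monitored. This is fair, but none of it reaches the primary result. The pilot offers limited reassurance because its tumours were palpable, while this study enrols tumours that palpation cannot define.

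Finally, there is no hypothesis test or success threshold in SAP 6.2.1, and the SAP is at version 0.1. That argues against treating this as a fatal fault.

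**Conclusion.** The point holds in two parts. The PMR denominator is unstated and the text conflicts; on its own this moves the rate by a few tenths of a point at most in the cases shown. Separately, a tumour missed by BCL guidance cannot enter the PMR numerator under either denominator, and each such patient is worth 2.86 points at N = 35. With one positive margin and one miss, the upper limit is 14.9% or 15.3% under the two readings of the plan, and 19.2% if the miss counts as a failure. Only the last exceeds the 18% that SAP 1.2.3 sets against the standard of care.

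This rests on assumed counts and an FAS of 35. The chance of a miss is very uncertain, at about 1% to 95%, because it comes from one event in 67 with a different technique. It also assumes that Appendix 1 is unchanged in protocol version 2.0, which the SAP cites; the protocol reviewed here is the November 2022 version. The documents do not show that misses will occur, nor that the primary endpoint must become a composite. Severity: should-fix.

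**What to change.** In SAP 6.2.1 and the Table 14 shell:

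1. State that the primary PMR and its exact interval use FAS patients with a margin assessment, in line with SAP 1.2.3, and footnote that denominator in the table.
2. Add a sensitivity analysis on all FAS patients, with an exact interval. Count as failures every positive margin, every BCL-guided specimen without the target cancer, and every unassessed margin.
3. Report beside the PMR the number of failed localizations (no tumour specimen removed, or no cancer in the BCL-guided specimen) and the number of unassessed margins. Add a no-tumour response to the lumpectomy histology item, or derive it from the pathology report.

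Counting misses in a sensitivity analysis keeps the primary endpoint as Appendix 1 defines it. Building them into the primary rate would change that definition and conflict with SAP section 7, which reports no changes from the protocol.

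The cost is a few SAP lines, some table rows and one data item. The sensitivity rate may look less favourable than the primary one.

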### Statistical Output Layout:

All tables will be presented for overall treatment group and all listings will be presented by patient ID, study visits and, if necessary, by study centers;

|   |                           |                  |                |
|---|---------------------------|------------------|----------------|
|  | Form               | Form Nr.  | 1M-DMST-011-A3 |
|   | Statistical Analysis Plan | Page      | 15 of 116      |
|   |                           | Version # | 0.1            |

The format for presentation of time variables will be hh:mm. The format for presentation of date variables will be dd/mmm/yyyy. Missing portions of dates will be represented on patients listings as dashed:

|                      |              |
|----------------------|--------------|
| Complete date | 15/Jan/2022  |
| Unknown day   | UNK/Jan/2022 |
| Unknown month | UNK/UNK/2022 |

Dates that are missing because they are not applicable for the patient will be presented as "UNK/UNK/UNK", unless otherwise specified.

Listings will be sorted by patient screening number unless specified otherwise.

|  |                           |                  |                |
|--|---------------------------|------------------|----------------|
|  | Form               | Form Nr.  | 1M-DMST-011-A3 |
|  | Statistical Analysis Plan | Page      | 16 of 116      |
|  |                           | Version # | 0.1            |

### 5.3. Visit Names and Labels

The names to be used in the analysis datasets and the labels to be used in the tables, listings and figures for the different study visits are defined below.

| Visit number | Visit name                | Visit label,
which appear in TLFs | Visit ID |
|--------------|---------------------------|--------------------------------------|----------|
| 01           | Screening & Enrollment V0 | Screening V0                         | V0       |
| 02           | Visit 1                   | V1                                   | V1       |
| 03           | Visit 2 Surgery           | Surgery V2                           | V2       |
| 04           | Visit 3 Follow-up         | Follow up V3                         | V3       |
| 05           | Visit 4 EOS               | EOS V4                               | V4       |

### 5.4. Visit Windows

In the study, 5 study visits were planned.

- The screening/baseline visit will be performed within 30 days before V1
- V1 will be performed at day 0
- V2 will be performed within 10/40 days from V1
- V3 will be performed at week 2  $\pm$  7 days from V2
- EOS visit will be performed after 6 weeks since V2  $\pm$  7 days.

### 5.5. Multiple testing

Not applicable for this study.

|  |                           |                  |                |
|--|---------------------------|------------------|----------------|
|  | Form               | Form Nr.  | 1M-DMST-011-A3 |
|  | Statistical Analysis Plan | Page      | 17 of 116      |
|  |                           | Version # | 0.1            |

## 6. Statistical Analysis: Definitions, Derivations, Calculations and Methodology

### 6.1. Baseline Characteristics

#### 6.1.1. Disposition of Patients

##### Collected Variables:

- Was Informed Consent signed? (Yes/No) [CRF – V0]
- If Yes, Informed Consent date (dd/mmm/yyyy) [CRF – V0]
- Visit date (dd/mmm/yyyy) [CRF – V0, V1, V2, V3, V4]
- Was surgery performed? (Yes/No) [CRF – V2]
- If Yes, date of surgery (dd/mm/yyyy) [CRF – V2]
- Has the patient completed the study? (Yes/No) [CRF – EOS]
- If Yes, specify date (dd/mm/yyyy) [CRF – EOS]
- If No, specify the reason for early termination or withdrawal (Screening failure/Consent withdrawal/Adverse event/Protocol violation/Lost to follow-up/Subject non-compliance/Death/Other) [CRF – EOS]
- Date of withdrawal (dd/mmm/yyyy) [CRF – EOS]
- If Death, please specify cause of death (free text) [CRF – EOS]
- If Other, please specify (free text) [CRF – EOS]

##### Derived Variables:

- Eligibility of the patient according to Inclusion/Exclusion criteria
- Date of study termination: the date of withdrawal or the date of study completion
- Whether the patient belongs to each different analysis sets and the reasons for exclusion from each set.

##### Imputations for missing values:

Not applicable.

|                               |          |              |
|-------------------------------|----------|--------------|
| Analysis Sets to be used for: | Tables   | All patients |
|                               | Listings | All patients |
|                               | Figures  | All patients |

Patients' data will be summarized as follows:

|  |  |
|--|--|
| Table 1. Disposition of the patients      | The total number of patients included in the different analysis and, in case of exclusion, reasons for exclusion from each analysis sets will be provided. |
| Table 2. Patients who completed the study | Frequencies tables of patients who completed the study. For patients who did not complete the study, reason of withdrawal will be provided.                |

|  |                           |                  |                |
|--|---------------------------|------------------|----------------|
|  | Form               | Form Nr.  | 1M-DMST-011-A3 |
|  | Statistical Analysis Plan | Page      | 18 of 116      |
|  |                           | Version # | 0.1            |

**Table 3.** Study status by visit      The number of patients taking part at each study visit will be provided.

Patients' data will be listed as follows:

**Listing 1A.** Disposition of the patients – Study participation      Listing of all patients with information about study participation: IC signature, eligibility, study termination status, eligibility in each dataset, and, if applicable, reason of exclusion from each dataset and/or of withdrawal.

**Listing 1B.** Disposition of the patients – Study dates      Listing of all patients and study dates of each step of the study: date of informed consent, visit dates, surgery date, study termination and/or withdrawal.

Patients' data will be represented as follows:

**Figure 1.** Disposition of the patients      The number of patients included in analyses data sets.

**Figure 2.** Status of study termination      The number of patients who completed the study as protocol and the number of patients who did not complete the study as protocol with withdrawal reason.

|  |                           |                  |                |
|--|---------------------------|------------------|----------------|
|  | Form               | Form Nr.  | 1M-DMST-011-A3 |
|  | Statistical Analysis Plan | Page      | 19 of 116      |
|  |                           | Version # | 0.1            |

